#### *Data Analysis.*

**fMRI data preprocessing.** fMRI data will be preprocessed using SPM8 to remove noise and artifacts, correct for slice acquisition time, motion corrected [14], temporally realigned using B-spline interpolation, normalized into standard stereotaxic space (MNI) with an isotropic 2mm voxel size and smoothed with an 8mm FWHM Gaussian filter. **Voxel-wise, within-mask analysis.** At the 1st-level, data will be analyzed using the GLM [15]. Each of 2 blocks of interest (Drug, Control) will be modeled as a boxcar canonically convolved hemodynamic response function, and in scanner heart-rate, respiration rate and motion parameters will be entered as nuisance covariates. Next, Drug-Control contrast images will be generated, entered into a 2nd-level, 2 (VRN: Yes, No) x 2 (NAC: Yes,

*Figure 3. ROI:* superior, middle, & inferior frontal gyri (SFG, MFG, IFG), dorso- & ventro-medial, ventrolateral and prefrontal cortex (dmPFC, vIPFC, vMPFC), anterior cingulate cortex (ACC), insula, amygdala, putamen, nucleus accumbens (NA), caudate & thalamus.

No) ANOVA, and analyzed within an ROI mask (Fig. 3),  $p < .05$ , corrected for multiple comparisons. fMRI data analysis plan: Resting-state functional connectivity will be assessed using the conn13 SPM8 toolbox. First, experimental design variables, pre-processed functional images filtered with a 0.01 to 0.08 Hz band-pass filter and normalized (modulated to preserve volume) T1 and segmented images will be uploaded into the toolbox. 5-mm spheres will be created around MNI coordinates for *a priori* regions of interest (ROIs) that include: bilateral amygdala, nucleus accumbens, dACC and inferior, middle and superior frontal gyri. The conn13 toolbox uses PCA to isolate potentially confounding noise from nuisance covariates using default settings. Individuals' WM and CSF templates, in-scanner heart-rate (HR), respiration rate and movement parameters will be included as covariates. Connectivity matrix for the nucleus accumbens and amygdala seeds will each be entered into separate: 2 (NAC: Yes, No) x 2 (VRN: Yes, No) ANOVAs. We will follow-up with exploratory whole brain analyses.

Brain-behavior data analysis plan: First, POMS, SJW and mCEQ subscale scores will be computed, and motivation to smoke and days to first cigarette (lapse) following the experimental visit will be recorded for each subject. Next, to examine the interactive effects of treatment on self-report and rsFC, each scale will be entered as a regressor of interest in separate between subjects ANOVA's in the Conn Toolbox.

Smoking topography analysis plan: Craving regulation performance will be assessed by calculating change scores (Later-Now) from craving ratings. T-tests will be performed to analyze correlations between craving ratings, smoking topography variables: time to 1st puff (i.e. task blocks); puff volume (milliliters) and number of puffs. Regression analyses will explore relations between SSRT performance and strength of rsFC between ROI's in Figure 11.

Real-world smoking behavior analysis: Number of days to lapse (DTL) following the lab visit on day 10 will be recorded. Regression analyses entering DTL on brain cue-reactivity and rsFC will be performed and relations explored.

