**Abstinence Period (Days 7-10).** Smoking abstinence from the target quit date (Day 7) until Day 10 will be confirmed via breath CO samples (abstinence <6 ppm). Participant diaries and medication packs will be reviewed for safety and compliance. Brief assessments on craving, mood and withdrawal symptoms will also be completed.

**fMRI -2 Experimental Visit (Day 10).** Participants will be contacted two days prior to the scheduled fMRI session and reminded of session-specific details. Participants will fill out questionnaires regarding mood, withdrawal symptoms, and caffeine, nicotine, and food intake over the last 24 hours. Expired CO and BAC will be collected to confirm compliance. While in the MRI scanner, participants will lie still while undergoing a high resolution anatomical scan, as well as perform the CR task. Participants will be inside of the MRI scanner for approximately one hour. After the scanning portion of the visit, the participant will complete the POB assessment followed by the participant performing the SRRT and smoking a cigarette through the CReSS smoking topography system. Participants will again be video recorded while smoking through the CReSS device for visual confirmation of the device data collection.

**Follow-Up Assessments (Days 11-35).** After the fMRI session, participants will continue to take study medication for another 18 days (Days 11-28). They will return to the clinic on Days 14, 21, 28, and 35 to submit expired CO and urine samples to determine smoking status and medication compliance, as well as complete mood, nicotine craving/withdrawal, and safety assessments. Participants will return to the clinic on Day 35 for a one-week post medication safety, smoking assessment, and POB.

At the discretion of the PI's additional urine drug screens, pregnancy, and cotinine tests can be added to a visit day in order to address any unexpected safety and or data integrity concerns within a participant's active participation within the protocol. As needed when urine cotinine collection is not feasible, saliva specimens will be collected for cotinine assay.

[figure not shown]
**Duration.** Participation in the study will take about 6 weeks with a total of 10 visits lasting approximately 13-14 hours in total. The first visit (screening/training) will last up to 4 hours; each of the 7 clinic visits (Days 7-9, 14-35) will last about 15 minutes each, and the fMRI Experimental visits (Day 0 and 10) will each last approximately 4 hrs.

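### The resting-state plan, read literally, band-pass filters the images before regressing out movement, heart rate and respiration, and does not say that these regressors get the same filter

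*Combined protocol and SAP*

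**What the plan says.** The relevant text is the fMRI data analysis plan in section C, Data Analysis. It opens with the inputs to the connectivity toolbox, which include "pre-processed functional images filtered with a 0.01 to 0.08 Hz band-pass filter"; these, with the design variables and the structural images, "images will be uploaded into the toolbox". After defining the regions of interest it turns to denoising: "The conn13 toolbox uses PCA to isolate potentially confounding noise from nuisance covariates using default settings". It then adds that "Individuals' WM and CSF templates, in-scanner heart-rate (HR), respiration rate and movement parameters will be included as covariates". The resulting values go to the treatment comparison: "Connectivity matrix for the nucleus accumbens and amygdala seeds will each be entered into separate" two-by-two ANOVAs (NAC yes/no by VRN yes/no).

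The plan does not say whether the movement, heart-rate and respiration series are filtered, whether the toolbox filters again, or what the default settings do. It gives no TR or resting-run length. The visit descriptions say only "Participants will be inside of the MRI scanner for approximately one hour".

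**The concern.** The stated sequence is filter, upload, regress. Once the images hold only 0.01 to 0.08 Hz, a regressor that still has power outside that band cannot be fitted properly to them. Its slope is shrunk, part of the in-band nuisance stays in, and out-of-band regressor signal is written into the residuals. Regions that share the same nuisance then look connected.

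Resting connectivity is the subject of Aim 1, and the power section names the effect of VRN+NAC on the BOLD signal as the primary aim. The connectivity values are also reused in the self-report, smoking-task and days-to-lapse analyses. Participants are scanned while nicotine deprived, and the background section expects VRN to reduce acute withdrawal. Arm differences in restlessness, heart rate or breathing are therefore conceivable, and leftover noise that differed by arm would bias the contrast.

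**Working it through.** The plan states no figure for residual nuisance signal, so there is nothing to reproduce.

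**Inputs.** From the plan: pass band 0.01 to 0.08 Hz, width 0.07 Hz. Assumed, because the documents are silent: TR 1 to 3 s, an 8-minute run, the nuisance spectra below, and regressors left unfiltered.

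**One regressor, algebra.** Let φ be the share of the regressor's variance V inside the band.
- Slope after filtering the data only: φ times the true slope.
- In-band residual variance: (1−φ)² × φV.
- Out-of-band variance written back: φ² × (1−φ)V.
- Sum: φ(1−φ)V × [(1−φ) + φ] = φ(1−φ)V.
- Divided by the original in-band variance φV: **1−φ**. Counting only what lies inside the band, as after a second band-pass, it is (1−φ)².

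For white noise, φ = 0.07 ÷ (1/(2·TR)) = 0.14 × TR:
- TR 1 s: φ = .14, left 86%; in band only .86² = 74%.
- TR 2 s: φ = .28, left 72%; in band only .72² = 52%.
- TR 3 s: φ = .42, left 58%; in band only .58² = 34%.

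**Eight regressors, simulation** (six motion, heart rate, respiration; 480 s; ideal filter; 200 runs per setting). Entries are residual nuisance variance as a share of the original in-band nuisance variance.

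| Nuisance spectrum | Regressors unfiltered | Unfiltered, then second band-pass | Regressors filtered to match |
|---|---|---|---|
| White, TR 1 s | 85% | 72% | 0% |
| White, TR 2 s | 69% | 49% | 0% |
| White, TR 3 s | 55% | 31% | 0% |
| AR(1), .5 to .95 per 2 s, TR 1–3 s | 34–49% | 14–32% | 0% |
| Random walk, TR 1–3 s | 53–55% | 38–39% | 0% |
| Already inside the band | 0% | 0% | 0% |

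The last row is the case of WM and CSF signals extracted from filtered images: they share the pass band, so the order of steps does them no harm.

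**Effect on a correlation.** Two regions with no true connectivity, half of each region's unfiltered variance being shared nuisance, TR 2 s; mean r with no regression, with unfiltered regressors, and with matched filtering:
- White: .50, .42, .00.
- AR(1) .8: .68, .43, −.01.

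Regressing first and filtering afterwards also gave r of about 0 (−.02 to .02) in every setting. A further simulation (TR 2 s, 180 volumes, spectra from white to 1/f^1.5, all assumed) gave r of .12 to .42 with the written order and unfiltered regressors, against about 0 with matched filtering.

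**Effect on the arm contrast.** With a true arm difference, nuisance equal across arms, 400 per arm and no tissue regressors, the standardised effect under the written order versus the matched filter was .70 v .69 (white), .59 v .62 (intermediate) and .78 v .75 (1/f^1.5). The differences are at most .03 and go in both directions.

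**The case against.** The strongest reply is that the plan never calls the covariates unfiltered. It leaves denoising to toolbox defaults that the documents do not describe, and the phrase about filtered images may be loose wording for a filter set inside the toolbox. That stands: the defect is conditional on how the pipeline is run.

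Second, WM and CSF covariates are in the model, and if taken from filtered images they are already in band. Adding two such signals to a simulation at TR 2 s and 180 volumes (nuisance about 25% of in-band variance, tissue noise SD half that of the shared signal) cut the spurious r from .15–.18 to .01–.03. This stands in part. The rescue works when the tissue signals carry nearly the same nuisance mixture as the regions (r of .00 to .05); with imperfect overlap r stays at .07 to .27.

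Third, the plan names heart rate and respiration rate, which plausibly vary slowly, so white noise is a poor model for them, and the images are also motion corrected in preprocessing. This argues for the lower part of the range, but the autocorrelated and random-walk rows still leave 34% to 55%.

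Fourth, Aim 1 compares randomised, double-blind arms, and leftover noise that is equal across arms largely cancels. The contrast figures above support this.

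**Conclusion.** The concern holds in limited form. Followed literally, the plan filters the images first and regresses out movement, heart rate and respiration afterwards, with no matching filter stated. Unless one is applied, nuisance variance equal to roughly 34% to 86% of what was in the band stays in the data. A second band-pass would lower this to 14% to 72% but not remove it. These figures rest on assumed TR, run length and spectra.

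A reader might infer more than the documents support:
- That the regressors are known to be unfiltered. The plan is silent.
- That most of the nuisance signal remains. This is so for white noise and marginally for random-walk drift, but not for the autocorrelated spectra.
- That the tissue signals suffer too. Taken from the filtered images, they do not.
- That the Aim 1 result is biased. That needs motion or physiology to differ by arm, and the documents give no such figure; with no difference the effect on the contrast is small.

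The point is therefore of moderate importance: a cheap improvement to the primary imaging measure, not a condition for the trial to proceed.

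**What to change.** In the fMRI data analysis plan (section C, Data Analysis), take the band-pass filter out of the list of uploaded inputs and state one of two sequences. Either unfiltered images are uploaded, nuisance regression is done first and the residuals are then filtered at 0.01 to 0.08 Hz; or the identical filter is applied to the images and to all regressors in one step. If the toolbox is already run in one of these ways, only the sentence needs correcting. It would help to name the default settings relied on and to give the TR and run length.

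Cost: one sentence and, at most, one pipeline setting. No new data are needed.

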## B. BACKGROUND AND SIGNIFICANCE

Cigarette (henceforth nicotine) addiction is a chronic, relapsing brain disorder and remains the leading preventable cause of death and disability in the US [1], costing nearly \$200 billion each year [2]. Although ~20% of adults in the USA currently smoke [3], the majority want to quit. In spite of the breadth of research focused on improving health outcomes and reducing the societal burden caused by nicotine addiction, the majority of smokers who attempt to quit will relapse. Nicotine withdrawal-related disturbances in executive function, negative affect and reward processes compel a smoker to self-administer nicotine—each in turn representing the loss of control to remain abstinent and risk factors for relapse [4]. Thus, identifying the effects of nicotine addiction on mechanisms of self-regulation, and the value of novel medications for remediating dysregulated behavior are both needed in order to enhance interventions for treating nicotine addiction. Our preliminary data, along with the extant literature, suggest that the maintenance of nicotine addiction is subserved by dysregulated neural function in limbic-striatal and corticostriatal neural circuitry. While VRN may be effective in treating limbic-striatal circuitry that is associated with promoting abstinence and reducing acute withdrawal; NAC may be effective in treating corticostriatal circuitry function that is associated with relapse vulnerability. Thus, the current proposal seeks to investigate two medications (VRN & NAC), with potentially complementary effects on the two different brain circuits—limbic-striatal (VRN) and corticostriatal (NAC) circuitry—and that may therapeutically target two different phases in the recovery of nicotine addiction—the promotion of abstinence (VRN) and relapse prevention (NAC). The placebo (PBO)-controlled design in this proposal will allow the team to identify and translate between the neurobiological substrates and the neurocognitive underpinnings of the effects of VRN+NAC on smoking behavior in humans—thus, advancing our understanding of the pathophysiology of nicotine addiction.

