*Exploratory Clinical Outcomes.* The clinical outcomes assessed in this study are designed to assess relapse for 3 weeks following a period of monitored abstinence under PBO-controlled medication conditions. Although the study is not specifically powered to detect the secondary hypothesis of an additive effect of VAR and NAC on abstinence from nicotine (2x2 interaction), the stated sample size will allow for the estimation of effect sizes and the precision of the variance in order to inform a subsequent larger study. Based upon completion rates in our prior studies, we anticipate a 15% attrition rate between randomization and the end of the clinical portion of the study; thus, we anticipate that 94 of the 150 randomized participants will provide secondary clinical data for analysis (23 in each treatment assignment). Assuming that no additive effect is present and that the NAC/PBO abstinence rate is 10%, we will have 80% power with a type 1 error rate of 5% to detect an abstinence rate of 33% in the VRN group.

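### The exploratory days-to-lapse regressions give no rule for participants without a lapse day and specify no treatment term for cue-reactivity

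*Combined protocol and SAP*

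**What the plan says.** Section C, Data Analysis, counts DTL from the Day 10 laboratory visit. The paragraph on real-world smoking behavior then says: "Regression analyses entering DTL on brain cue-reactivity and rsFC will be performed and relations explored". The type of regression is not named.

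The preceding brain-behavior paragraph says that "days to first cigarette (lapse) following the experimental visit will be recorded for each subject". It gives no value for someone who has not smoked by the end of follow-up and no rule for someone lost before lapsing.

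Treatment appears in three nearby places:
- The brain-behavior paragraph says that, "to examine the interactive effects of treatment on self-report and rsFC, each scale will be entered as a regressor of interest". This concerns rsFC, and lapse is covered only if it counts as a scale.
- In the cue-reactivity model, "Drug-Control contrast images will be generated, entered into a 2nd-level, 2 (VRN: Yes, No) x 2" NAC ANOVA. DTL is not in that model.
- The Protocol Overview states a general intent to examine treatment conditions together with fMRI measures and smoking behavior over the following three weeks. It gives no model.

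The Exploratory Clinical Outcomes paragraph under Power Calculation and Sample Size expects both kinds of participant without a lapse day. It says "we anticipate a 15% attrition rate between randomization and the end of the clinical portion of the study", and its power statement begins "Assuming that no additive effect is present and that the NAC/PBO abstinence rate is 10" percent and is "to detect an abstinence rate of 33% in the VRN group".

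**The concern.** A participant still abstinent at the end of follow-up has no lapse day, only a lower bound for it. A plain regression needs a number. One analyst may leave the value blank, so that software drops the participant. Another may enter the last day of the window. Both follow the text and can reach different answers. Dropping would remove mainly VRN participants, because VRN is expected to produce more abstinence.

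The treatment question is separate. The Background says "VRN may be effective in treating limbic-striatal circuitry that is associated with promoting abstinence". If VRN both shifts the brain measure and delays lapse, pooling the arms without a treatment term can show a brain-lapse relation when none exists within any arm. The plan does not say whether it wants the pooled or the within-arm relation.

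The end of the window is also not named. Three weeks from Day 10 is Day 31. Medication ends on Day 28 (28 - 10 = 18 days), and the last smoking assessment is on Day 35 (35 - 10 = 25 days).

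**Working it through.** **Inputs from the plan.** 94 participants with clinical data, abstinence 10% without VRN and 33% with VRN, 80% power, 5% type 1 error, 15% attrition (all from Exploratory Clinical Outcomes), and 18 days from the Day 10 scan to the end of medication (Follow-Up Assessments).

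**Reproducing the plan's own figure.** Comparing 47 on VRN with 47 off VRN, two-sided .05, pooled variance under the null:

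z = [.23 x sqrt(47) - 1.96 x sqrt(2 x .215 x .785)] / sqrt(.10 x .90 + .33 x .67) = (1.577 - 1.139) / .558 = .785, so power is 78%, close to the stated 80%.

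With 23 per side the same formula gives 47%. The split of 47 against 47 is therefore the one that fits the plan, and it is used below.

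**How many have no lapse day.** This reads the abstinence rates as lapse-free rates. It is an assumption, because the plan gives no definition or assessment day for abstinence. It is an upper bound.
- Off VRN: 47 x .10 = 4.7
- On VRN: 47 x .33 = 15.5
- Total: 20.2 of 94 (21.5%), with 15.5 / 20.2 = 77% on VRN

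If the rates are halved, the total is about 10 of 94.

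**What the handling rule does to power.** Simulation with 10,000 datasets per scenario, n = 94, NAC crossed with VRN, one uncorrected two-sided test at .05. Lapse times are exponential with daily hazards -ln(.10)/18 = .128 off VRN and -ln(.33)/18 = .062 on VRN, multiplied by exp(b x) for a standardised brain measure x. The values of b and the constant hazard are assumptions. Ranges reflect whether the rates hold on average over x or at its mean.

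| Scenario (18-day window, no arm terms) | Drop non-lapsers | Cap at window end | Cox |
|---|---|---|---|
| b = .3 | 19-20% | 61% | 64% |
| b = .4 | 30-33% | 83-84% | 85-86% |
| b = .5 | 44-48% | 95-96% | 96-97% |
| b = .4, abstinence rates halved | 51-55% | 90% | 91-92% |
| b = .4, n = 128 | 43% | 93% | 94% |

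The n = 128 row is there because 15% attrition from 150 leaves 150 x .85 = 127.5, not 94. With arm terms at b = .4 and n = 94, capping gives 86% and Cox 90-91%.

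**What leaving out treatment does.** Here b = 0 within arms, and the brain measure is shifted on VRN by an assumed amount.

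| VRN shift in brain measure | Pooled, capped | Pooled, Cox |
|---|---|---|
| .4 SD | 9% | 10% |
| .6 SD | 13% | 14% |
| .8 SD | 19% | 21% |

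With VRN, NAC and VRN x NAC in the model, the rates are 5% (capped) and about 6% (Cox, a slight small-sample excess of the Wald test). With halved abstinence rates, the pooled capped figures are 7%, 10% and 12-13%.

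**The case against.** Several points on the other side are sound.

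- **Treatment is not absent from the plan.** A reader might infer that it is ignored wherever lapse is related to the brain. The documents do not support that. The Protocol Overview states the intent to examine it, and the brain-behavior paragraph names treatment interactions for rsFC. What is missing is a specified term: wholly for cue-reactivity, partly for rsFC.
- **The large power loss is not planned.** A reader might infer that the analysis would lose most of its power. That follows only from dropping non-lapsers, which no section proposes, and recording DTL for every subject points the other way. Under capping, the cost against Cox is a few points.
- **The pooled relation may be of interest.** The Background proposes that VRN works through circuitry tied to abstinence, so an association carried by treatment is not simply an error. The plan does not say which relation is meant. The 9% to 19% is a false-positive rate only for the within-arm question.
- **The percentages describe one uncorrected test under assumed effects.** The plan corrects the ROI-mask analysis for multiple comparisons. With a Bonferroni correction over an assumed 14 tests, capped power at b = .4 is about 52%. The d = .8 in the power section comes from smoking-abstinence and NAC studies, not VRN, so the VRN shift is an assumption.
- **The analysis is exploratory.** The Figure 1 text labels it so. Aims 1 and 2 do, however, include relations with maintenance of abstinence.

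None of this supplies a rule for participants without a lapse day or a model containing treatment.

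**Conclusion.** The point holds as a gap in an exploratory analysis. The regressions treat DTL as though everyone has a lapse day, and lapse with cue-reactivity has no specified treatment term. On the plan's own rates, read as lapse-free rates, about 20 of 94 participants are affected, unevenly by arm.

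At an assumed log hazard ratio of .4 per SD, the unstated choice moves power between about 30% (drop) and 84% to 86% (cap or Cox). With an assumed VRN shift of .4 to .8 SD and no within-arm relation, the pooled capped analysis is significant in about 9% to 19%, against about 5% with arm terms. The textual gap does not depend on these assumptions, but its size does. The primary imaging comparisons are not affected. The change should be made before analysis, but its severity is modest.

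**What to change.** Add to the analysis plan:

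1. **Definition.** DTL is days from the Day 10 visit to the first cigarette outside the laboratory task. The cigarette smoked through the CReSS device at the end of that visit does not count. State how participants who were not abstinent through Days 7-10 enter.
2. **Censoring.** Censor at last contact or at the end of treatment (Day 28), whichever comes first. As sensitivity analyses, extend the window to Day 35 and count loss as lapse, because censoring at last contact assumes that loss is uninformative.
3. **Model.** For extracted ROI and connectivity values, fit a Cox model of DTL on the brain measure with VRN, NAC and VRN x NAC, the factors already in the second-level ANOVA. Correct for multiple comparisons as the Data Analysis section requires for the ROI-mask analysis. In voxel-wise regressions, cap DTL at the window end and include the same arm terms.
4. **Companion result.** Report the unadjusted pooled relation alongside, labelled as including treatment effects.

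The cost is some wording, a little more analysis work and three degrees of freedom. The sponsor should also check that lapse dates are collected after Day 10. The protocol introduces a daily diary on Day 0 but mentions diary review only for Days 7-10, and the appendix lists a diary review and a 30-day cigarette timeline without visit days.
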